7.14 Schedule of Procedures and Observations

The schedule of procedures and observations for this study is summarized in **Table 4** below.

Table 4. Schedule of Procedures and Observations

Tests and Procedures	Screening (≤ 14 Days Prior to Initiation of Study Drug)	Cycle 1		Prior to treatment on Day 1 of Subsequent Cycles (± 3 days)	30 Day Follow- Up (± 7 days)	Survival Follow- Up
		Day 1	Weekly ¹ (± 2 days)			
Informed Consent	X					
Medical History	X ²	X ³	X ³	X ³	X ³	
Physical Exam, (including vital signs, body weight, height) ⁴	X	X	X	X	X	
ECOG Performance Status	X	X	X	X	X	
Adverse Event Evaluation	X	X ⁵	X	X	X	
Tumor Assessment	X ⁶			X ⁷		
CT Scan/MRI Brain	X ⁸					

Tests and Procedures	Screening (≤ 14 Days Prior to Initiation of Study Drug)	Cycle 1		Prior to treatment on Day 1 of Subsequent Cycles (± 3 days)	30 Day Follow- Up (± 7 days)	Survival Follow- Up
		Day 1	Weekly ¹ (± 2 days)			
Pregnancy Test (urine or serum)	X ⁹					
Coagulation (INR, PTT)	X					
Hematology (4 hour fasting) ¹⁰	X	X	X	X	X	
Chemistry (4 hour fasting) ¹¹	X	X	X	X	X	
Pharmacogenetic Blood Sample		X ¹²				
12-Lead ECG ¹³	X			X ¹⁴		
Survival Follow-Up						X ¹⁵

- 1 Patients will be evaluated weekly during Cycle 1 only. Complete physical examination is not mandatory but will be performed as needed at the discretion of the treating physician.
- 2 Full medical history.
- 3 Updated medical history from previous clinical visit.
- 4 Height collected at baseline only.
- 5 Reassess the patient for adverse events just prior to administration of the first dose of study drug on Day 1 Cycle 1. (Reassess adverse events on Day 1 of subsequent cycles and modify dose if necessary according to the dose modification **Table 3**, if clinically indicated, for Grade 2 or higher adverse events).
- 6 Imaging studies such as chest x-ray, CT scans, PET-CT, and MRIs can be performed ≤ 28 days prior to initiation of study drug. Use same imaging throughout the study. Assessment by physical exam should be done ≤ 14 days prior to initiation of study drug. If using PET-CT, use the CT portion to obtain measurements.
- 7 Tumor assessment must be performed at least every other cycle after completing Cycle 2. Tumor assessment may be performed ± 3 days prior to treatment on Day 1 of subsequent cycles. Tumor assessment should be performed at any time during the treatment cycle that disease progression is clinically suspected so that patient can go off treatment and receive other therapy. If PET-CT was used at baseline, CT only may be used for subsequent cycles.
- 8 Brain imaging is required in symptomatic patients to rule out brain metastases, but is not required in asymptomatic patients.
- 9 Women of childbearing potential only. Must be done ≤ 7 days prior to initiation of study drug.
- 10 Hematology (i.e., complete blood count (CBC) with automated differentials or the physician discretion; WBC, RBC, HGB, HCT, platelet, MCV, MCH, MCHC, %neutrophils, absolute neutrophils, %lymphocytes, absolute lymphocytes, %monocytes, absolute monocytes, %eosinophils, absolute eosinophils, %basophils, absolute basophils, %Large Unspecified Cells (LUC), %lymphocyte total, absolute lymphocyte total, platelet confirmation, and differential confirmation).
- 11 Chemistry (i.e., complete metabolic panel (CMP): chloride, CO₂, potassium, sodium, BUN, glucose, calcium, creatinine, total protein, albumin, total bilirubin, alkaline phosphatase, AST, ALT, A/G ratio, BUN/creatinine ratio, osmol (Calc), anion gap).
- 12 Pharmacogenetic blood sample collection will be obtained at Day 1 of Cycle 1.
- 13 The patient will be asked to lie down and rest for about 10 minutes before this procedure.
- 14 Prior to Cycle 2 and Cycle 3, if clinically indicated.
- 15 Survival follow-up assessments may be collected via telephone.

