	
≤ 14 days prior to initiation of study drug, Cycle 1 (Day 1 and weekly), and prior to treatment on Day 1 of subsequent cycles, 30-Day Follow-Up.
 
Performance Status: ≤ 14 days prior to initiation of study drug, Cycle 1 (Day 1 and weekly), and prior to treatment on Day 1 of subsequent cycles, 30-Day Follow-Up.
 
12-Lead ECG: ≤ 14 days prior to initiation of study drug and prior to treatment on Day 1 of Cycle 2 and Cycle 3, if clinically indicated.

Statistical Analysis
	
Efficacy Assessments:
 
 • 18-week PFS is defined as the proportion of patients whose disease has not progressed at 18 weeks after getting etirinotecan pegol. • Tumor response is defined as a complete response (CR) or partial response (PR) by RECIST 1.1 criteria, which will be evaluated by CT-scan every other cycle. • OS is defined as the time from enrollment to death from any cause. 
Safety Assessments:
 
 • The maximum grade for each type of adverse events (AEs) will be recorded for each patient based on NCI CTCAE version 4.0, and frequency tables will be reviewed to determine AE and toxicity (unrelated, unlikely, possible, probably, or definitely related to study treatment) patterns in each group. • A single-stage design will be used to assess the primary endpoint separately for each. Based on this, the primary endpoint of this trial will be the proportion of patients who are progression-free at 18 weeks.

Study Schema

INVESTIGATOR STUDY ELIGIBILITY VERIFICATION FORM

Subject Name: (Network sites use subject initials): _____

Medical Record No.: (Network sites use subject ID): _____

Title: A Phase II Study of Single Agent Topoisomerase-I Inhibitor Polymer Conjugate, Etirinotecan Pegol (NKTR-102), in Patients with Relapsed Small Cell Lung Cancer

INCLUSION CRITERIA				
Yes	No	N/A	All answers must be "YES or "N/A" for patient enrollment.	Date
			1. Written informed consent granted prior to initiation of any study-specific screening procedures, given with the understanding that the patient has the right to withdraw from the study at any time, without prejudice.	
			2. 18 years of age or older.	

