7.2.1 Retreatment Criteria

To ensure safe use of NKTR-102, subjects must meet requirements with respect to hematopoietic function (Hgb \geq 8.0 g/dL; ANC \geq 1.5×10^9 /L; platelets \geq 75×10^9 /L) prior to initiation of subsequent cycles. Diarrhea must be fully resolved to Grade 0 for at least 7 days without supportive antidiarrheal measures prior to retreatment. Any non-hematologic toxicities must have resolved to baseline or Grade 1 except for alopecia. Supportive care may be implemented in order to ameliorate diarrhea, nausea, vomiting, or myelosuppression. Dose reductions may also be implemented for subjects who experience recurrent or specific severe toxicities.

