7.2.2 Treatment Delay

If the patient fails to meet the criteria for re-treatment, treatment may be delayed, followed by an additional evaluation to determine feasibility of retreatment. Initiation of subsequent doses may be delayed for a maximum of 28 days to allow recovery from any toxicity to permit retreatment. Subjects whose treatment delays are \geq 14 days but \leq 28 days due to a drug-related toxicity must initiate their next treatment cycle with a dose reduction. Subjects who require $>$ 28 days delay due to unresolved toxicity must be withdrawn from treatment, unless, in the Investigator's opinion, continuing in the study is of benefit for the patient. In this case, the reason of continuation must be documented.

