11 STATISTICAL METHODOLOGY

11.1 Sample Size Determination and Analysis

In a Phase II and Phase III study of single agent topotecan or single agent irinotecan as shown in **Table 1** in recurrent SCLC, the median time to progression of the arms were 2.2 - 4 months.^{6,8-12} Based on this, the primary endpoint of this trial will be the proportion of patients who are progression-free at 18 weeks. Progression-free survival was chosen as the primary endpoint, rather than response rate, as this is appropriate clinical endpoint for cytotoxic agents such as NKTR-102 and for SCLC. A single-stage design will be used to assess the primary endpoint for each patient group. A treatment success was defined as a patient who was progression-free at 18 weeks. To evaluate Group A, the largest success proportion where the proposed treatment regimen would be considered ineffective in this population is 5%, and the smallest that would warrant further subsequent studies is 25%. Twenty evaluable patients will be entered on this study. If 2 or fewer successes are observed, this regimen will be considered ineffective in this patient population. If 3 or more successes are observed, this will be considered evidence that this treatment may be recommended for further testing in subsequent studies. Assuming that the

number of successes is binomially distributed, this design controls the Type I Error to be $< 10\%$ and has 90% power to detect 25% 18-week PFS rate. To evaluate Group B, the largest success proportion where the proposed treatment regimen would be considered ineffective in this population is 10%, and the smallest that would warrant further subsequent studies is 35%. Eighteen evaluable patients will be entered on this study. If 3 or fewer successes are observed, this regimen will be considered ineffective in this patient population. If 4 or more successes are observed, this will be considered evidence that this treatment may be recommended for further testing in subsequent studies. Assuming that the number of successes is binomially distributed, this design controls the Type I Error to be $< 10\%$ and has 90% power to detect 25% 18-week PFS rate. Patients who come off study (e.g., due to toxicity) and start an off-protocol therapy prior to 18 weeks will be considered failures at that point.

The evaluable population is defined as patients who meet eligibility requirements and receive any protocol treatment. Unevaluable patients will be replaced.

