Progression-free survival is defined as the time from registration to the date of first documented disease progression or death. Survival time is defined as the time from registration to death due to any cause. Patients who loss-to-follow-up or alive at time of analysis will be censored at the last contact of known alive. The distribution of time to disease progression and survival time will be estimated in each group using the method of Kaplan–Meier. Probability of PFS at 18 weeks and 24 week and probability of survival at 3, 6, and 9 months will be estimated. All eligible and treated patients will be included in the analysis of the primary endpoint.

All adverse events, regardless of attribution, will be summarized (overall and by group).³⁴

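### Tumor scans follow treatment cycles, but success is judged at a fixed 18 weeks; when dosing runs late no scan is required by then, and no rule for the binary endpoint classifies progression first seen afterwards

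*Combined protocol and SAP*

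**What the plan says.** **Endpoint.** Section 11.1: "A treatment success was defined as a patient who was progression-free at 18 weeks". Eighteen weeks is 126 days. The rule calls for 3 or more successes among 20 patients in Group A and 4 or more among 18 in Group B.

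**Scans.** Footnote 7 to Table 4 (section 7.14) says "Tumor assessment must be performed at least every other cycle after completing Cycle 2" and adds "Tumor assessment may be performed ± 3 days prior to treatment on Day 1 of subsequent cycles". Section 7.11 also schedules imaging every other cycle, and section 8.4 places it at the end of a cycle. Footnote 7 asks for an extra scan whenever progression is clinically suspected.

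**Delays.** Cycles last 21 days ± 3 (section 7.1). Section 7.2.2: "Initiation of subsequent doses may be delayed for a maximum of 28 days to allow recovery from any toxicity to permit retreatment". Section 7.2.1 gives a likely trigger: "Diarrhea must be fully resolved to Grade 0 for at least 7 days without supportive antidiarrheal measures prior to retreatment".

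**Dating and time origin.** Section 11.1: "Progression-free survival is defined as the time from registration to the date of first documented disease progression or death". The synopsis instead counts patients "whose disease has not progressed at 18 weeks after getting etirinotecan pegol". The only explicit classification rule for the binary endpoint, in 11.1, makes a patient who leaves study and starts other therapy before 18 weeks a failure.

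**The concern.** A fixed-time endpoint needs an assessment at that time, or a rule for when there is none. This plan requires neither. A patient whose dosing has slipped may have a clean scan at about day 84 and the next one only after day 126. If that later scan shows progression, the true status at day 126 is unknown and the plan supports two answers:

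- Under the PFS definition, progression is dated when first documented. That date is after 18 weeks, so the patient counts as a success.
- If the post-Cycle 6 scan is taken as the 18-week assessment, the same patient is a failure.

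The first reading favors the drug, because a delay, typically for toxicity, can turn unseen progression into a success. Such delays are foreseeable: section 1.3.2 gives a median of 93 days to onset of Grade 3 diarrhea on this schedule, between the day 84 and day 126 scans.

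**Working it through.** **1. The plan's own figures (exact binomial, 11.1).**
- Group A, n = 20, success if X ≥ 3: P(X ≥ 3 | p = 0.05) = 0.0755; P(X ≥ 3 | p = 0.25) = 0.909.
- Group B, n = 18, success if X ≥ 4: P(X ≥ 4 | p = 0.10) = 0.0982; P(X ≥ 4 | p = 0.35) = 0.922.

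Both type I errors agree with the text, which says "this design controls the Type I Error to be" below 10%. Group B has almost no room to spare.

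**2. When the deciding scan falls.** Take Cycle 1 Day 1 as day 0. With no delay, scans after Cycles 2, 4 and 6 are due on days 42, 84 and 126. If Cycle 7 Day 1 falls d days late in net terms, after any use of the ± 3-day cycle tolerance, the window is 126 + d ± 3.

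| Net delay d (days) | Scan window (days) | Wholly after day 126? |
|---|---|---|
| 0 | 123–129 | no |
| 3 | 126–132 | no |
| 4 | 127–133 | yes |
| 14 | 137–143 | yes |
| 28 | 151–157 | yes |

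Even on time, days 127–129 of the window lie past 18 weeks. The cycle tolerance alone could put Cycle 7 Day 1 anywhere from day 6 × 18 = 108 to day 6 × 24 = 144. Counted from registration, a 4-day gap before first dose gives a window of 127–133 with no dose delay at all.

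**3. Illustrative effect on type I error.** Assumptions, none of them from the documents:
- PFS is exponential and passes through the null rate p0 at day 126.
- Late-seen progression counts as success.
- A share g of the progressions between days 84 and 126 is missed in this way.

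Then S(84) = p0^(84/126), and the effective null rate is p0 + g × [S(84) − p0].
- Group A: S(84) = 0.05^(2/3) = 0.1357; excess 0.1357 − 0.05 = 0.0857.
- Group B: S(84) = 0.10^(2/3) = 0.2154; excess 0.2154 − 0.10 = 0.1154.

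| g | A: null rate | A: type I error | B: null rate | B: type I error |
|---|---|---|---|---|
| 0 | 0.0500 | 7.5% | 0.1000 | 9.8% |
| 0.05 | 0.0543 | 9.2% | 0.1058 | 11.5% |
| 0.10 | 0.0586 | 10.9% | 0.1115 | 13.3% |

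**4. The opposite convention.** If late-seen progression counts as failure and half of patients are scanned 7 days late, the same exponential form gives power of 0.893 (A, 25% rate) and 0.908 (B, 35% rate). The cost is small and falls on the drug's side.

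**The case against.** The strongest reply is that six 21-day cycles make exactly 126 days, so the post-Cycle 6 scan was plainly meant as the 18-week assessment. Read that way, progression on it is a failure, type I error is not inflated, and step 4 shows little loss of power. This is a sensible reading, but the plan does not state it.

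The following also stands:
- The PFS definition leads into the Kaplan–Meier analysis and is not expressly linked to the success count, so a bias toward the drug is a default reading and not a stated rule.
- Footnote 7 permits a scan on day 126 while Cycle 7 is held. It does not require one.
- Scans on clinical suspicion, and the section 8.4 rule that symptomatic deterioration counts as progression, will catch some cases early.
- The exponential null implies median PFS of about 29 days (A) and 38 days (B), against the 2.2–4 months cited in 11.1. It indicates direction better than size.

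A reader might infer that any 4-day dose delay pushes the scan past week 18. It does not. Suppose diarrhea starts on day 93 and clears on day 102, so Cycle 6 is given on day 109. Cycle 7 may then be given on day 127 within tolerance, and the window of days 124–130 includes day 126.

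A reader might also infer that type I error control has failed, perhaps by using the 23% Grade 3 diarrhea rate in the breast cancer study as the share missed. That figure is neither a delay rate nor a rate of unseen progression, and the documents give no such share.

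**Conclusion.** The gap is real. Followed as written, the plan can leave day 126 status resting on the day 84 scan, with no stated rule for progression first found later and two different time origins. One reclassified patient can reverse either group's conclusion. That much follows from the text and the calendar.

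The effect on type I error cannot be determined. The increases for g of 5% and 10% (to 9.2% and 10.9% in Group A, 11.5% and 13.3% in Group B) hold only under the exponential curve and the count-as-success reading. That Group B passes 10% so readily reflects its starting value of 9.8% more than a large effect. This is a cheap improvement worth making to the primary endpoint, not a demonstrated failure of the design.

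**What to change.** **Footnote 7, with 7.11 and 8.4 aligned.** Scan at weeks 6, 12 and 18 (days 42, 84 and 126 from Cycle 1 Day 1, each ± 3 days), then every 6 weeks. Dose delays do not move the scans. Continue scans to week 18 in patients who stop treatment without progression or new therapy; Table 4 currently has no tumor assessment after treatment, so it needs an entry for this.

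**Section 11.1.**
- Count 18 weeks from Cycle 1 Day 1, and match the synopsis.
- Progression first documented on the week 18 scan (days 123–129) is a failure.
- If that scan is missed, progression on the next scan is a failure and a clean next scan is a success.
- A patient with no scan at or after week 18 is a failure.

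The Kaplan–Meier estimate at 18 weeks is already planned and needs no addition.

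**Cost.** Some off-cycle visits, and scans after stopping treatment for a few patients. In the extreme case that every week 18 scan fell on day 129, the exponential assumption gives success rates of 0.25^(129/126) = 0.2419 and 0.35^(129/126) = 0.3414. Power would go from 90.9% to 89.5% in Group A and from 92.2% to 91.0% in Group B, a loss of at most about 1.4 points.

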1.5 Risks Associated with NKTR-102

A majority of NKTR-102 related treatment-emergent adverse events (TEAEs) occurred in the system organ class (SOC) of GI disorders with diarrhea experienced most commonly by 85.5% of patients, followed closely by nausea (77.6%), fatigue (51.3%), and vomiting (48.7%). Other clinically significant NKTR-102-related TEAEs with an incidence rate > 10% included anorexia, dehydration, alopecia, electrolyte disturbances like hypokalemia and hypomagnesemia,

abdominal pain, anemia, and blurred vision, in decreasing order of frequency. Prolonged severe diarrhea with dehydration leading to pre-renal azotemia and subsequent acute renal insufficiency has been fatal in three patients in the ongoing Phase II studies in metastatic colorectal, ovarian, and breast cancers (one patient in each study). To date, early onset cholinergic diarrhea (as seen with irinotecan) has not been observed in any patient who received NKTR-102. Given the extended $t_{1/2}$ of SN38 derived from NKTR-102 (approximately 50 days), late onset diarrhea may occur and can be life-threatening if treatment is delayed. Early, proactive, and aggressive intervention with anti-diarrheal therapy, IV hydration, and maintenance of electrolyte balance is essential to prevent volume depletion, electrolyte imbalances, and the development of kidney failure.

Myelosuppression, especially neutropenia, can occur in patients receiving NKTR-102. Neutropenia in the setting of dehydration and unresolving GI toxicities may lead to the development of life-threatening or fatal sepsis. To date across all clinical studies, three patients have died within 30 days from last dose of NKTR-102 due to potentially drug-related neutropenic sepsis or complications of neutropenic sepsis, such as septic shock.

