7.2.3 Dose Reductions

NKTR-102 doses for an individual patient may be reduced 25 mg/m² based on conditions listed in the **Table 3** below. Only 2 dose reductions are permitted. Subjects should be discontinued from the study treatment if toxicity requires a dose reduction beyond the 2 dose reduction steps. Dose re-escalation for NKTR-102 is not permitted.

Table 3. Dose Modifications Based on Toxicities

Toxicity NCI CTCAE Grade	During a Cycle: Recommended Guidelines for Management and Supportive Care	Day 1 of New Cycle: Dose Modifications Based on Worst Toxicity in Prior Cycle
Thrombocytopenia / Anemia / Neutropenia / Febrile Neutropenia		
Grade 1 or Grade 2	-	Maintain dose level

Grade 3
	
Platelets: consider platelet transfusion if active bleeding.
 
ANC: consider growth factor support in accordance with local guidelines.
 
Hgb: erythropoietin-stimulating agents or transfusion as appropriate.
 
If present on a treatment day, hold therapy for a week or until toxicity resolves to Hgb \geq 8 g/dL or 80 g/L; ANC \geq 1.5×10^9/L; platelets \geq 75×10^9/L, with a maximum of 28 days.
	
↓ 1 dose level after 1st occurrence. ↓ 1 dose level after 2nd occurrence. Discontinue patient after 3rd occurrence.

Grade 4
	
Platelets: consider platelet transfusion if platelets < 20K or with active bleeding.
 
ANC: consider growth factor support in accordance with local guidelines.
 
Antibiotic (Fluoroquinolones) should be initiated even in the absence of fever or diarrhea.
 
Hgb: consider erythropoietin-stimulating agents or transfusion as appropriate.
 
If present on a treatment day, hold therapy for a week or until toxicity resolves to Hgb \geq 8 g/dL or 80 g/L; ANC \geq 1.5×10^9/L; platelets \geq 75×10^9/L, with a maximum of 28 days.
	
↓ 1 dose level after 1st occurrence. ↓ 1 dose level after 2nd occurrence. Discontinue patient after 3rd occurrence.

Febrile Neutropenia
	
Subjects should be hospitalized immediately for IV antibiotic therapy if they develop neutropenic fever or sepsis (e.g., growth factor support; antibiotics); consider hospital admission.
	
↓ 1 dose level after 1st occurrence. ↓ 1 dose level after 2nd occurrence. Discontinue patient after 3rd occurrence.

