
Diarrhea Any Grade
	
Institute supportive care upon first loose stool. (Unless contraindicated, use loperamide). Monitor bowel function; if diarrhea continues with 1st supportive care agent, consider switching to a 2nd agent or add a 2nd agent (unless contraindicated, use diphenoxylate/atropine).
 
Monitor for dehydration, electrolyte abnormalities; correct if present.
 
Administer antibiotic therapy (oral fluoroquinolones) if the patient develops ileus, fevers or Grade 3/4 neutropenia.
 
Subjects should be immediately hospitalized for IV antibiotics therapy if they have evidence of colitis or ileus even in the absence of neutropenia or fever.
 
If worsening diarrhea, octreotide may be attempted.
 
Monitor bowel function for continued need of supportive care.
 
Stop supportive care after the patient is 48 hour without diarrhea.
	
Confirm with the patient that diarrhea is no longer present for ≥ 7 days without having received supportive care prior to retreatment.
 
Treatment may be delayed up to 28 days; after this, contact Medical Monitor.

Grade 1
	
If still present within 7 days prior to treatment hold therapy until diarrhea is no longer present for ≥ 7 days without having received supportive care.
	
Maintain dose level; consider prophylactic anti-diarrheal supportive care

Grade 2
	
If still present within 7 days prior to treatment hold therapy until diarrhea is no longer present for ≥ 7 days without having received supportive care.
	
↓ 1 dose level after 1st occurrence. ↓ 1 dose level after 2nd occurrence. Discontinue patient after 3rd occurrence.

Grade 3/4
	
If still present within 7 days prior to treatment hold therapy until diarrhea is no longer present for ≥ 7 days without having received supportive care.
	
↓ 2 dose level after 1st occurrence. Provided that adequate supportive care has been given to the patient, discontinue patient after 2nd occurrence. If the patient has not received adequate supportive care, retreatment may be attempted for a 2nd episode of Grade 3 diarrhea (re-instruct patient on supportive care). Patients must be discontinued for a 2nd episode of Grade 4 diarrhea.

Dehydration		

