7.3 Concomitant Medication and Supportive Care

7.3.1 Anti-Emetic Therapy

Prophylactic anti-emetics will be allowed according to standard practices.

Based on investigator discretion, an investigator may prescribe prophylactic antiemetics prior to the first dose of the study drugs. The patient must be carefully monitored throughout the study period, and given adequate fluid and electrolyte replacement to prevent dehydration and electrolyte imbalance. Dexamethasone, ondansetron, lorazepam or prochlorperazine can be given at the discretion of the treating physician.

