5. Patients who are dehydrated must promptly receive adequate IV fluids, electrolytes to combat electrolyte imbalance if present and antibiotics in case of fever. Serial complete and differential blood counts must be done for early identification of the concomitant occurrence of neutropenia.

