7.8 Baseline Evaluations

The following will be performed \leq 14 days prior to initiation study drug:

- Informed consent: Must be completed prior to receiving any study-related procedures.
- Medical history (Full history)
- Physical examination, including vital signs, body weight, and height
- ECOG performance status
- Adverse events evaluation

- Tumor assessment by CT/PET or CT scan should be performed within 28 days prior to initiation of study drug
- CT scan/MRI brain (brain imaging is required in symptomatic patients to rule out brain metastases, but not required in asymptomatic patients)
- Pregnancy test (urine or serum) in females of childbearing potential. Must be done ≤ 7 days prior to initiation of study drug.
- Coagulation (INR, PTT)
- Hematology (4 hour fasting) (i.e., complete blood count (CBC) with automated differentials or the physician discretion; WBC, RBC, HGB, HCT, platelet, MCV, MCH, MCHC, %neutrophils, absolute neutrophils, %lymphocytes, absolute lymphocytes, %monocytes, absolute monocytes, %eosinophils, absolute eosinophils, %basophils, absolute basophils, %Large Unspecified Cells (LUC), %lymphocyte total, absolute lymphocyte total, platelet confirmation, and differential confirmation)
- Chemistry (4 hour fasting) (i.e., complete metabolic panel (CMP): chloride, CO₂, potassium, sodium, BUN, glucose, calcium, creatinine, total protein, albumin, total bilirubin, alkaline phosphatase, AST, ALT, A/G ratio, BUN/creatinine ratio, osmol (Calc), anion gap)
- 12-Lead ECG. The patient will be asked to lie down and rest for about 10 minutes before this procedure.

7.9 Evaluations Performed on Cycle 1 Day 1

- Medical history (Updated from previous clinical visit)
- Physical examination, including vital signs and body weight
- ECOG performance status
- Adverse events evaluation
- Hematology (4 hour fasting) (i.e., complete blood count (CBC) with automated differentials or the physician discretion; WBC, RBC, HGB, HCT, platelet, MCV, MCH, MCHC, %neutrophils, absolute neutrophils, %lymphocytes, absolute lymphocytes, %monocytes, absolute monocytes, %eosinophils, absolute eosinophils, %basophils, absolute basophils, %Large Unspecified Cells (LUC), %lymphocyte total, absolute lymphocyte total, platelet confirmation, and differential confirmation)

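### Hypomagnesemia is a named drug-related risk, but the scheduled chemistry panel measures potassium and not magnesium

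*Combined protocol and SAP*

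**What the plan says.** Section 1.5 says that further drug-related events of clinical significance "with an incidence rate > 10% included anorexia, dehydration, alopecia, electrolyte disturbances like hypokalemia and hypomagnesemia". Those are the only two electrolyte disturbances it names.

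The scheduled chemistry is spelled out after 'i.e.', so it reads as a full definition and not as examples. Table 4, footnote 11, gives "Chemistry (i.e., complete metabolic panel (CMP): chloride, CO₂, potassium, sodium, BUN, glucose, calcium, creatinine, total protein, albumin, total bilirubin, alkaline phosphatase, AST, ALT" and then the A/G ratio, BUN/creatinine ratio, calculated osmolality and anion gap. Section 7.8 has the same list ("Chemistry (4 hour fasting) (i.e., complete metabolic panel (CMP): chloride, CO₂, potassium, sodium, BUN, glucose, calcium, creatinine" and so on), as do 7.9, 7.10, 7.11 and 7.12.

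Three places deal with electrolytes in general terms:
- Section 7.3.1, under anti-emetics: "The patient must be carefully monitored throughout the study period, and given adequate fluid and electrolyte replacement to prevent dehydration and electrolyte imbalance".
- Section 7.3.2, item 5, for patients already dehydrated: "electrolytes to combat electrolyte imbalance if present".
- Table 3, diarrhea of any grade: "Monitor for dehydration, electrolyte abnormalities; correct if present".

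Two rules act on non-hematologic toxicity at the start of a cycle. Section 7.2.1 requires it to be back to baseline or Grade 1. Table 3's catch-all row for other drug-related non-hematologic toxicity holds dosing when Grade 2 or worse is present on a treatment day. Section 11.5 evaluates non-hematologic toxicity by CTC grade.

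**The concern.** The protocol names a pair of electrolyte risks and schedules a test for only one of them. A site that orders exactly the listed panel complies with Table 4 and may never measure magnesium.

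Two things are at stake, both modest. The first is patient care: the retreatment check and the treatment-day hold cannot act on a low magnesium value that nobody has obtained. The second is reporting. Toxicity is a secondary objective and Section 4.2 plans multiple sites. If magnesium is tested only when a clinician thinks of it, the reported frequency of hypomagnesemia will partly reflect ordering habits.

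**Working it through.** The plan gives no figure to reproduce. The check sets the risk text beside every place where a magnesium test could be scheduled.

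**1. Contents of the panel.** Footnote 11 lists 14 measured items (chloride, CO₂, potassium, sodium, BUN, glucose, calcium, creatinine, total protein, albumin, total bilirubin, alkaline phosphatase, AST, ALT) and 4 derived items (A/G ratio, BUN/creatinine ratio, osmolality, anion gap): 14 + 4 = 18. Magnesium is not among them and cannot be derived from them.

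**2. Consistency across visits.** The list appears six times: 7.8, 7.9, 7.10, 7.11, 7.12 and footnote 11. Potassium is in 6 of 6 and magnesium in 0 of 6, so this is not a slip in one table.

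**3. Other scheduled tests.** Coagulation, hematology, pregnancy test, ECG, imaging and the pharmacogenetic sample do not measure magnesium.

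**4. Scheduled draws per patient.** Assume that the weekly Cycle 1 visits after Day 1 are Days 8 and 15.
- Treated through Cycle 6: 1 screening + 1 Cycle 1 Day 1 + 2 weekly + 5 (Day 1 of Cycles 2 to 6) + 1 follow-up = 10.
- Stopped after Cycle 2: 1 + 1 + 2 + 1 + 1 = 6.

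Potassium is measured at each of these 6 to 10 draws and magnesium at none. Ten is toward the upper end, since Section 11.1 cites median times to progression of 2.2 to 4 months for the comparators.

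**5. Reach of the general text.**

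| Place | Who is covered | Names magnesium? | Sets a schedule? |
|---|---|---|---|
| 7.3.1 | All patients, within anti-emetic guidance | No | No |
| 7.3.2, item 5 | Dehydrated patients | No | No |
| Table 3, diarrhea row | Patients with diarrhea of any grade | No | No |

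These provisions leave a magnesium test to the clinician. What remains uncovered is low magnesium without symptoms that no one decides to test for.

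**6. Rules affected.** The resolution check in 7.2.1 and the treatment-day hold in Table 3 both need to know the current grade. With no value, neither can act.

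**7. What reaches the safety tables.** Section 9.1.1.3 records a laboratory abnormality as an adverse event only if it is clinically significant and needs active management. Section 9.1.1.2 lets an event secondary to diarrhea be recorded under diarrhea alone. Both apply to potassium as well as magnesium. Section 11.5 plans analysis of laboratory values only for hematologic measures. Adding the assay alone would therefore leave unmanaged abnormalities of either electrolyte out of the tables.

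**The case against.** The strongest reply is that the protocol deliberately leaves electrolyte care to clinicians and makes it obligatory. Section 7.3.1 has no diarrhea trigger and asks for replacement that prevents imbalance. Table 3 and 7.3.2 add duties during diarrhea and dehydration. Nothing bars extra tests. This stands as far as it goes: magnesium will be measured in some patients. A reader might infer that the trial has no electrolyte safeguard or that magnesium will never be checked, and the text does not support that. But a general duty of care is not a scheduled measurement, and it does not give comparable ascertainment across sites.

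A second reply is that potassium is not cleanly ascertained either, because recorded hypokalemia also passes through site judgment under 9.1.1.2 and 9.1.1.3. That is correct. The contrast is between measured and unmeasured, not between well reported and badly reported, and a summary for magnesium alone would be lopsided.

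A third reply is that routine testing has treatment consequences. Under Table 3, drug-related Grade 3 or 4 values lead to one dose level down after each of the first two occurrences and discontinuation after the third. Section 7.2.2 forces a reduction after a drug-related delay of 14 to 28 days. Section 7.2.3 allows two reductions and no re-escalation. Asymptomatic laboratory values could therefore lower dosing. This is a real cost and has to be weighed.

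**Conclusion.** The gap is real and small. A risk that the protocol names is absent from every scheduled panel, and the general text does not fill the gap systematically. Confidence is high on the omission and lower on its consequences.

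Four stronger readings are tempting and are not supported:
- **A count of missed cases.** Applying 10% to 38 patients gives 38 × 0.10 = 3.8, and an assumed 30% gives 11.4. But the figure in 1.5 may describe electrolyte disturbances as a group, no dose or schedule is stated for it, and the documents give no rate of unscheduled testing. An expected case is also not a missed case.
- **A split by diarrhea.** Section 1.5 reports "diarrhea experienced most commonly by 85.5% of patients", which might be used to divide patients into those covered by Table 3 and those not. That counts diarrhea, not magnesium tests. Dehydration has its own care text, and 7.3.1 covers everyone.
- **Failure of the dose rules as a whole.** Table 3 sets the next dose under the column "Dose Modifications Based on Worst Toxicity in Prior Cycle", so a reduction does not rest on the Day 1 value alone. The Grade 1 limb of 7.2.1 works without a baseline value. Only the resolution check and the treatment-day hold are affected, and only for untested patients.
- **A threat to the efficacy conclusion.** The 18-week endpoint, the success thresholds and the sample size do not use magnesium.

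This is an optional, low-priority improvement to safety monitoring.

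**What to change.** Add serum magnesium to the chemistry list in Sections 7.8, 7.9, 7.10, 7.11 and 7.12 and in Table 4, footnote 11. In Section 11.5, add a summary of the worst CTCAE grade per patient, taken from laboratory values, for both potassium and magnesium.

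The blood is already drawn, so no visit or procedure is added. The costs are a small laboratory charge, an amendment line and the added summary. There will also be some extra magnesium replacement and some Day 1 holds for Grade 2 or higher values. For drug-related Grade 3 or 4 values, Table 3 dose reductions are possible, with discontinuation after a third occurrence. The sponsor should accept those dosing consequences knowingly when making the change.
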